4. STUDY DESIGN

4.1. Overall Design

This study is a multi-site, open-label clinical trial validating the SpO₂ accuracy and precision of Medline's reprocessed pulse oximetry sensors as compared to SaO₂ in arterial blood samples as assessed by CO-oximetry in neonates. The data collection will take place at the sites. The PI or designee will place the Masimo and Nellcor sensors on hands and/or feet of the subject according to the IFU and record the reading. The arterial blood sample used in this study will be taken in the normal course of care and will be measured in the reference CO-oximeter for SaO₂. This arterial sample will be obtained from a systemic artery.

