8.3. Populations for Analysis

All data pairs will be included for analysis, unless at the time of data acquisition any one or more of the following is true: (1) the SpO2 value is >100%; OR (2) the SpO2 value is \leq 0%; OR (3) the heart rate measurement derived from the pulse oximeter is 0 beats per minute; OR (4) the research personnel collecting the data notes an anomaly in the measurement on the CRF at the time of data collection before data analysis begins. Any such designated outliers and/or anomalous data will be explained and any data that is excluded from the analysis will be justified in the final report.

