8.4 Data Analysis

Accuracy of each pulse oximeter will be assessed per ISO 80601-2-61:2017, the FDA "Pulse Oximeters - Premarket Notification Submissions [510(k)s] Guidance for Industry and Food and Drug Administration Staff" document issued on March 4, 2013, and paper by Bland et al., 2007.^{3,4,5}

For each pulse oximeter, an accuracy root mean square (A_{RMS} , in equation 1.1 below) will be calculated to define the SpO₂ accuracy compared to the SaO₂ as measured by co-oximeter, as outlined in ISO 80601-2-61:2017 sub clause 201.12.1.101. It is expected that each of the sensors should achieve an $A_{RMS} \leq 3\%$ as per the testing of these same products in the protocol on adult subjects. In addition, mean Bias (B, in equation 1.2) defined per ISO 80601-2-61:2017 as the mean difference between the test and reference values, preserving sign, and precision (SD_{res} , in equation 1.3), defined per ISO 80601-2-61:2017 as the standard deviation of the residuals.

In the following equations, let

- SpO_{2_i} be the oxygen saturation value for the i^{th} data pair in the range of interest measured using the pulse oximeter
- SaO_{2i} be the reference oxygen saturation value for the *i*th data pair in the range of interest measured using the co-oximeter
- and *n* be the number of data pairs in the sample in the range of interest.

Then, per ISO 80601-2-61:2017 A_{RMS} is defined as:

$$A_{RMS} = \sqrt{\frac{\sum_{i=1}^{n} (SpO_{2_i} - SaO_{2_i})^2}{n}}$$
(1.1)

Mean bias B is defined as:

$$B = \frac{\sum_{i=1}^{n} (SpO_{2_i} - SaO_{2_i})}{n}$$
(1.2)

And precision (SD_{res}) is defined as:

$$SD_{res} = \sqrt{\frac{\sum_{i=1}^{n} (SpO_{2_i} - SpO_{2fit_i})^2}{n-2}}$$
(1.3)

where SpO_{2fit_i} is the difference between the *i*th datum and the value of the fitted curve corresponding to the *i*th reference value

For each pulse oximeter, a Bland-Altman plot (mean vs. difference of SaO_2 and SpO_2) and an error plot (SaO_2 vs. difference of SaO_2 and SpO_2) will be generated. Between and within subject variance and upper and lower 95% limits of agreement will be presented. Subject demographic data will be presented with summary statistics and site-level effects will be assessed as appropriate. Outliers will be explained and any data that is excluded from the data analysis or any deviations from this statistical analysis plan will be justified in the final report.

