9.2.3 Data Handling and Record Keeping

Data collection is the responsibility of the clinical trial staff at the site under the supervision of the PI. The PI is responsible for ensuring the accuracy, completeness, legibility, and timeliness of the data reported.

All source documents of any kind (electronic, paper, etc.) should be completed in accordance with Good Documentation Practices (GDP) to ensure accurate interpretation of data. CRFs will be created for each subject. The CRA will verify the data entered into the CRF with the site source regardless of the type of source. The site will be responsible for developing a written process that ensures the CRA is able view the source data.

Data from the CRFs will be entered by Medline into an electronic spreadsheet via dualentry to assure no errors. Data will be transferred to and analyzed with Statistical Analysis System (SAS), SAS[®] 9.4, for statistical analysis. SAS[®] allows for internal quality checks, such as automatic range checks, to identify data that appear inconsistent, incomplete, or inaccurate. Medline Industries, Inc. will be responsible for performing final data analysis and confirmation of results.

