| model Onder Test | 70 – 100 | 90 – 100 | 80 – 90 | 70 – 80 | |
| Adtx 1859 Arms ^a | 1.8 | 1.1 | 1.8 | 2.2 | |
| Neo 2329 Arms | 1.6 | 0.9 | 1.6 | 2.1 | |
| ^a A _{rms} = average root mean square. | | | | | |

Figures 6 and 7 provide graphical representation of sample data points acquired during the adult clinical trial using the Medline ReNewal Reprocessed Masimo LNCS SpO₂ Sensors.

Fig. 6: Bland-Altman plot of all sampled data points by subject for the adult clinical study for the Medline ReNewal Reprocessed Masimo Adtx 1859 sensor with linear regression fit and upper and lower 95% limits of agreement.

Fig.7: Bland-Altman plot of all sampled data points by subject for the adult clinical study for the Medline ReNewal Reprocessed Masimo Neo 2329 with linear regression fit and upper and lower 95% limits of agreement.

WARNINGS

Single use devices cannot be reused. If devices are to be used again, they must be returned to Medline ReNewal for reprocessing. Please see Medline ReNewal instructions to healthcare facilities before returning.

The names of actual companies and products mentioned herein may be the trademarks of their respective owners.

Medline ReNewal Reprocessed Nellcor™ OxiMax SpO2 Sensors Models MAXA, MAXAL, MAXP, MAXI, and MAXN

Instructions for Use

*Read the Instructions for Use in their entirety before using Medline ReNewal Reprocessed Nellcor™ OxiMax SpO2Sensors.

Failure to comply may result in patient and/or healthcare-staff injury.

| Description: | Reprocessed device for single use. Reprocessed by Medline ReNewal. |
|---------------------|----------------------------------------------------------------------------------|
| Non Sterile: | The device is supplied non sterile. |
| Caution: | Federal (USA) law restricts this device to sale by or on the order of a |
| Contact: | physician. For more information please call Medline ReNewal Customer Service: |
| Contact. | [name]. |

DESCRIPTION

Medline ReNewal Reprocessed Nellcor OxiMax SpO2 Sensors. Following clinical use, each sensor is returned to Medline ReNewal where it is cleaned, disinfected, and packaged for an additional clinical use. Each sensor is tracked through the reprocessing cycle to monitor the number of times the sensor has been reprocessed.

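### Rule (4) of section 8.3 excludes pairs on an anomaly judgement with no stated criteria, and no result with those pairs included is planned

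*Combined protocol and SAP*

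**What the plan says.** Section 8.3 (Populations for Analysis) includes every pair unless, at data acquisition, one of four conditions holds. Rules (1) to (3) can be checked from recorded numbers: SpO₂ above 100%, SpO₂ at or below 0%, or a pulse-oximeter heart rate of zero. Rule (4) applies when "the research personnel collecting the data notes an anomaly in the measurement on the CRF at the time of data collection before data analysis begins".

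For excluded data, section 8.3 promises that "Any such designated outliers and/or anomalous data will be explained" and that "any data that is excluded from the analysis will be justified in the final report". Section 8.4 repeats the commitment: "Outliers will be explained and any data that is excluded from the data analysis" is to be justified in the final report. Section 8.4 otherwise plans A_RMS, bias, precision and limits of agreement once per sensor. On the target it says "It is expected that each of the sensors should achieve an" A_RMS of at most 3%.

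Section 4.1 describes a "multi-site, open-label clinical trial". Section 9.2.3 adds a check on the records: "The CRA will verify the data entered into the CRF with the site source".

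**The concern.** Rule (4) is the only exclusion that rests on judgement, and the person who judges is the one taking the reading. The instructions for use in the appendix list causes of inaccurate readings, such as a misapplied or dislodged sensor, motion, low perfusion, ambient or bilirubin light, and a low-signal message. Rule (4) points to none of them.

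The existing safeguards are useful. A contemporaneous note before analysis guards against deletion once results are known, source verification confirms that the CRF entry agrees with the site source, and the report must justify each exclusion. None of them sets the criterion for an anomaly. A written justification also does not give the reader the A_RMS that would have been obtained with the pairs kept.

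This matters because A_RMS squares each error. If excluded pairs tend to have large errors, a few of them can carry much of the statistic.

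**Working it through.** **Planned size.** Section 8.1 doubles 40 pairs to 80 per sensor. With at most three pairs per subject, 80/3 = 26.7, which rounds up to the stated 27 subjects. Both figures reproduce.

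**Inputs.** The number of pairs is 80 (section 8.1, a minimum). The adult A_RMS over 70–100% saturation is 1.6 for the Masimo sensor (appendix, Masimo instructions, Table 3: "Neo 2329 Arms | 1.6 | 0.9 | 1.6 | 2.1", first figure) and 1.7 for the Nellcor MAXN (appendix, Nellcor instructions, Table 2). The number of rule-(4) pairs, k, and their error size, e, are not documented. They are assumptions and are shown over a range.

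**Effect of putting pairs back.** From equation 1.1, if 80 − k kept pairs have A_RMS a and k excluded pairs have error e:

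A_RMS(all) = √{[(80 − k)·a² + k·e²] / 80}

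Example with a = 1.6, k = 4, e = 12: (76 × 2.56 + 4 × 144)/80 = 770.56/80 = 9.632, and the square root is 3.10.

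| k | e (points) | a = 1.6 | a = 1.7 |
|---|---|---|---|
| 2 | 12 | 2.47 | 2.53 |
| 3 | 12 | 2.80 | 2.86 |
| 4 | 12 | 3.10 | 3.15 |
| 5 | 10 | 2.94 | 2.99 |
| 6 | 10 | 3.14 | 3.19 |

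If 80 is the number analysed and four further pairs were excluded, the k = 4, e = 12 values become 3.05 and 3.10, still above 3.

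**Error size that takes A_RMS to exactly 3.** Solving for e gives e = √{[720 − (80 − k)·a²]/k}.

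| A_RMS of kept pairs | k = 2 | k = 4 | k = 8 |
|---|---|---|---|
| 1.6 (adult) | 16.1 | 11.5 | 8.2 |
| 1.7 (adult) | 15.7 | 11.2 | 8.0 |
| 2.5 (assumed) | 10.8 | 7.8 | 5.8 |

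At adult performance the excluded errors must be large. If the kept pairs already give 2.5, smaller errors are enough.

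**Upper-bound illustration.** Simulate 80 independent, zero-mean normal errors and remove the four largest in absolute size. The chance that the observed A_RMS is at most 3 then changes as follows:

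- True A_RMS 3.2: from 23% with none removed to 81%. Removing four at random leaves it at 23%.
- True A_RMS 3.5: from 4% to 42%.
- True A_RMS 1.7: about 100% either way. The mean reported value falls from 1.70 to 1.49.

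Picking out exactly the largest errors would need knowledge of SaO₂, so these figures bound the effect for four removed pairs under this model and do not estimate it for this trial. The model also ignores correlation among up to three pairs from one subject.

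**The case against.** The strongest reply is that exclusions are already contemporaneous, verified against source and justified, and that at the adult accuracy the 3% expectation is not in danger. Crossing 3 at k = 4 needs errors of about 12 points, roughly seven times the adult A_RMS (12/1.7 = 7.1; 12/1.6 = 7.5). This stands as a limit on size. It does not dispose of the point, because the appendix states saturation accuracy for these two models in adults only, and neonatal accuracy is what the study sets out to establish.

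Second, some exclusions are legitimate. The Masimo instructions indicate use without motion and in well-perfused patients, and the Nellcor instructions contraindicate low-perfused patients. Pairs flagged for these reasons lie outside labelled conditions, and restoring them mixes conditions of use with sensor error. This stands, and it is why the added analysis needs counts by cause and cannot replace the planned one.

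Third, section 8.3 ties the exclusion to the time of acquisition, so flagging a pair later, after comparing it with SaO₂, would depart from its wording. This stands in part: the text does not say whether the SaO₂ result may already be known within that time.

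Fourth, the CRF is not among the supplied documents and may already carry an anomaly list. The absence of criteria is therefore a statement about the supplied text only.

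A reader might also infer from "Any such designated outliers and/or anomalous data will be explained" that rule (4) lets staff drop a reading merely because it looks wrong. The documents do not support that. The sentence covers all four rules, and it sets outliers and anomalous data side by side, so the outlier label may equally describe rules (1) and (2).

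**Conclusion.** The point holds in a narrow form. Rule (4) is a judgement-based exclusion in an open-label study, with no criteria in the supplied text and no explicit requirement that the note precede sight of SaO₂. No result with the affected pairs included is planned, so the reported A_RMS cannot be tested against them.

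The size is conditional on undocumented quantities. With 80 pairs and the rest at 1.6–1.7, four pairs with 12-point errors move A_RMS above 3 and three do not. If the sensors perform as in adults and large errors are rare, nothing changes against 3%, and the added analysis would show that.

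Two stronger readings should be resisted. The 3% figure is an expectation with no hypothesis test or pass/fail rule, so the exclusions do not overturn a formal decision. Nor do the documents show that exclusions will in fact favour the sensors: no anomaly rate is given, and some exclusions would be for sound technical reasons. This is a cheap improvement, not a defect that undermines the design.

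**What to change.** (a) Require each rule-(4) note to state a technical cause, chosen from the causes in the appended instructions for use (for example misapplied or dislodged sensor, motion, low perfusion or low-signal message, ambient or bilirubin light) or entered as other with a specification. Require the note before the SaO₂ result is seen. A blood-sample or analyser fault may surface later, so record it separately on documented evidence of the fault and not on the difference between SpO₂ and SaO₂.

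(b) Keep the planned analysis. For each sensor, add a sensitivity analysis that gives A_RMS, bias, precision and limits of agreement with all rule-(4) pairs put back that have a valid numeric reading, meaning that rules (1) to (3) do not apply. Give the number of such pairs by stated cause, so that pairs outside the labelled conditions can be told apart from unexplained readings, and comment if the two A_RMS values fall on different sides of 3%.

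The cost is a few lines in section 8, a small CRF addition and one repeat analysis per sensor, with no new measurements. If the CRFs are already complete, the restored-pairs results in (b) can still be produced from the recorded data, with causes given as far as the notes state them. The downsides are that the all-pairs A_RMS may be less favourable, and that the open category leaves some judgement, which the comparison makes visible.

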8.4 Data Analysis

Accuracy of each pulse oximeter will be assessed per ISO 80601-2-61:2017, the FDA "Pulse Oximeters - Premarket Notification Submissions [510(k)s] Guidance for Industry and Food and Drug Administration Staff" document issued on March 4, 2013, and paper by Bland et al., 2007.^{3,4,5}

For each pulse oximeter, an accuracy root mean square (A_{RMS} , in equation 1.1 below) will be calculated to define the SpO₂ accuracy compared to the SaO₂ as measured by co-oximeter, as outlined in ISO 80601-2-61:2017 sub clause 201.12.1.101. It is expected that each of the sensors should achieve an $A_{RMS} \leq 3\%$ as per the testing of these same products in the protocol on adult subjects. In addition, mean Bias (B, in equation 1.2) defined per ISO 80601-2-61:2017 as the mean difference between the test and reference values, preserving sign, and precision (SD_{res} , in equation 1.3), defined per ISO 80601-2-61:2017 as the standard deviation of the residuals.

In the following equations, let

- SpO_{2_i} be the oxygen saturation value for the i^{th} data pair in the range of interest measured using the pulse oximeter
- SaO_{2i} be the reference oxygen saturation value for the *i*th data pair in the range of interest measured using the co-oximeter
- and *n* be the number of data pairs in the sample in the range of interest.

Then, per ISO 80601-2-61:2017 A_{RMS} is defined as:

$$A_{RMS} = \sqrt{\frac{\sum_{i=1}^{n} (SpO_{2_i} - SaO_{2_i})^2}{n}}$$
(1.1)

Mean bias B is defined as:

$$B = \frac{\sum_{i=1}^{n} (SpO_{2_i} - SaO_{2_i})}{n}$$
(1.2)

And precision (SD_{res}) is defined as:

$$SD_{res} = \sqrt{\frac{\sum_{i=1}^{n} (SpO_{2_i} - SpO_{2fit_i})^2}{n-2}}$$
(1.3)

where SpO_{2fit_i} is the difference between the *i*th datum and the value of the fitted curve corresponding to the *i*th reference value

For each pulse oximeter, a Bland-Altman plot (mean vs. difference of SaO_2 and SpO_2) and an error plot (SaO_2 vs. difference of SaO_2 and SpO_2) will be generated. Between and within subject variance and upper and lower 95% limits of agreement will be presented. Subject demographic data will be presented with summary statistics and site-level effects will be assessed as appropriate. Outliers will be explained and any data that is excluded from the data analysis or any deviations from this statistical analysis plan will be justified in the final report.

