8 STATISTICAL CONSIDERATIONS

8.1 Sample Size Determination

Data from a study assessing the accuracy of both pulse oximeters on an adult population (Study ID # 2018-268) were used as parameters for sample size estimation for this protocol. Sample size estimation was conducted separately for each product using both the Confidence Intervals for One Standard Deviation Using Standard Deviation (as an estimate for the accuracy root mean square A_{RMS} statistic in equation 1.1 below) and Bland-Altman procedures in PASS 2020 Power Analysis and Sample Size Software (2020). NCSS, LLC. Kaysville, Utah, USA, ncss.com/software/pass. The most conservative estimate between the two products for the A_{RMS} sample size (18) and the Bland-Altman statistic (40) was used as the minimum number of data pairs, n. A data pair will consist of a pulse oximeter sensor reading paired with an ABG reading collected by a CO-oximeter. We selected a sample size of at least 80 total data pairs for each of the two product sensors, consisting of at least 40 data pairs per site per product sensor. We doubled this estimate and selected a sample size of at least 80 total data pairs per product sensor, such that no subject contributes more than three data pairs for each of the two product sensors, for a minimum of 27 subjects. The same blood gas value can be used for multiple sensors applied simultaneously.

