8.2 Randomization

Randomization will not be completed as the data are collected from a convenience sample of subjects.

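### Section 8.4 compares one pooled A_RMS per sensor with an expected 3% but plans no confidence interval for it, although 8.1 sized the study with an interval procedure.

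*Combined protocol and SAP*

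**What the plan says.** Section 8.4 computes one A_RMS for each sensor over its pairs (equation 1.1). The benchmark reads "It is expected that each of the sensors should achieve an" A_RMS of 3% or less, justified "as per the testing of these same products in the protocol on adult subjects". It is worded as an expectation, and no decision rule is attached.

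The other planned outputs are mean bias, precision as the residual SD about a fitted curve, a Bland-Altman plot, an error plot against SaO2, a look at site effects, and this: "Between and within subject variance and upper and lower 95% limits of agreement will be presented". The section lists no confidence interval for A_RMS and no count, bias or A_RMS by saturation level.

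Section 8.1 sized the study with two procedures: a confidence interval for one SD, used as an estimate of A_RMS (18 pairs), and Bland-Altman (40 pairs). It then doubled the 40 to at least 80 pairs per sensor, "such that no subject contributes more than three data pairs for each of the two product sensors, for a minimum of 27 subjects". Section 8.2 says that "the data are collected from a convenience sample of subjects".

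On range, 8.4 defines n to "be the number of data pairs in the sample in the range of interest" and gives no limits. Section 8.3 states: "All data pairs will be included for analysis, unless at the time of data acquisition any one or more of the following is true". The listed exceptions are an SpO2 above 100% or not above 0%, a heart rate of zero, and an anomaly noted at collection. Section 8.4 also says: "Accuracy of each pulse oximeter will be assessed per ISO 80601-2-61:2017". It further cites an FDA guidance and a paper on agreement with repeated observations.

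**The concern.** The objective is to validate accuracy, and A_RMS against 3% is the only numerical benchmark. A point estimate just under 3% would meet the expectation even though the data are also compatible with a true value above it, and nothing planned would put a figure on that. Limits of agreement describe where individual differences fall. Variance components describe the sources of spread. Neither says how precisely A_RMS itself is known. The omission is odd because the interval was one of the two bases for the sample size.

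A second, smaller issue is case mix. Blood is drawn in normal care and nothing spreads the pairs across saturations. If most pairs lie above 90%, the pooled figure may say little about lower saturations. The error plot would show that by eye, without a count or a number.

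**Working it through.** **The plan's own figures.** 2 × 40 = 80 pairs, and 80/3 = 26.7, rounded up to 27 subjects. Both reproduce. The underlying 18 and 40 cannot be checked because their inputs are not given. An SD of 2.0 with a two-sided 95% upper limit of at most 3.0 would give 18 (upper limit 2.998), but that is a guess at unstated inputs.

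**Inputs.** 80 pairs, 27 subjects, at most three pairs each (8.1); benchmark 3% (8.4); adult A_RMS over 70-100% of 1.6 (Neo) and 1.7 (MAXN), from the IFU tables in the Appendix. Assumed, because the documents do not give them: normal errors, zero bias, ICC of the errors from 0 to 0.8, and the saturation mix.

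**Interval for A_RMS.** Limits are observed × sqrt(df/χ²), with χ² at its 97.5% and 2.5% points and df = 80/(1 + 2 × ICC²) for about three pairs per subject.

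| ICC | df | 95% CI, observed 3.0 | 95% CI, observed 1.7 | Observed value at which upper limit = 3 |
|---|---|---|---|---|
| 0 | 80 | 2.60-3.55 | 1.47-2.01 | 2.54 |
| 0.3 | 67.8 | 2.57-3.61 | 1.46-2.04 | 2.50 |
| 0.5 | 53.3 | 2.52-3.70 | 1.43-2.10 | 2.43 |
| 0.8 | 35.1 | 2.43-3.91 | 1.38-2.22 | 2.30 |

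For example, at ICC 0 the upper limit is 3 × sqrt(80/57.15) = 3.55. Observed values from about 2.54 (ICC 0) or 2.30 (ICC 0.8) up to 3.0 meet the expectation while the interval reaches above it.

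**Chance that the point estimate is 3 or less** (100,000 simulated studies per setting; range over ICC 0 to 0.8):
- true 3.2: about 23-33%
- true 3.5: about 4-12%
- true 4.0: at most 1.4%

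**Case mix.** Pooled A_RMS = sqrt(w × a² + (1 − w) × b²), where w is the share of pairs above 90%, a is A_RMS there and b is A_RMS below. With w = 0.9, a = 1.5 (the adult MAXN value for 90-100%) and an assumed b = 5: sqrt(0.9 × 2.25 + 0.1 × 25) = sqrt(4.525) = 2.13. With w = 0.7, 0.8 and 0.95 the result is 3.01, 2.61 and 1.84.

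At the adult band values themselves, equal thirds give 1.61 (Neo) and 1.72 (MAXN), matching the tabulated 1.6 and 1.7. A 90/8/2% mix over 90-100, 80-90 and 70-80 gives 1.01 and 1.51. All are well under 3.

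**The case against.** **The 3% is only an expectation, and adult accuracy is far below it.** This stands. A reader might infer that the plan has a pass/fail rule that would wrongly clear an inaccurate sensor; 8.4 contains no such rule. If neonates resemble adults, the interval lies wholly below 3 and the conclusion does not change. But the IFUs give the ±2% accuracy of these two models for adults only, so neonatal accuracy is the open question.

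**Sparse low saturations would be seen anyway.** Largely true. A reader might infer that figures by saturation band would catch what the pooled value and its interval miss. The numbers do not support that. In simulations with 8 of 80 pairs at an assumed A_RMS of 5 and the rest at 1.5 or 0.9, the interval for the pooled value reached above 3 in about 60-93% of studies. With the rest at 1.5, at least one low-saturation error exceeded 5 points in 87-95%, which the planned error plot and explanation of outliers would usually bring out. An A_RMS of 5 is also about 2.4 to 3.3 times the adult values of 1.5-2.1 below 90%. What remains is that the plot gives no count and no figure.

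**Sections 8.3 and 8.4 do not conflict.** A reader might infer a contradiction between the all-pairs rule and the range of interest. Section 8.3 lists invalid readings and 8.4 defines notation. The cited standards, which cannot be seen here, may set the range or bands, and both IFUs give an SpO2 range of 70-100%. This is a matter of clarification.

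**Conclusion.** The point holds for the missing interval. Section 8.4 should report the uncertainty of the statistic it uses to define accuracy. The consequence is confined to a neonatal A_RMS clearly worse than the adult one: observed values of roughly 2.3-3.0, where the interval may reach above 3. A true value as high as 4.0 would rarely read 3 or less. The sizes rest on 80 pairs from 27 subjects, normal errors, zero bias and ICC 0 to 0.8.

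The dependence on saturation mix is real but secondary. It rests on an assumed mix and an assumed low-saturation error, and supports a descriptive addition only. The undefined range of interest does not carry the point. The change is worth making because it is cheap and bears directly on what the study can conclude; it does not suggest that the design is unsound.

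**What to change.** 1. In 8.4, add a 95% confidence interval for each sensor's A_RMS that allows for up to three pairs per subject, and read the 3% expectation together with it. A studentised log-scale bootstrap that resamples subjects is one option. State its limitation: at a true 3.0, its upper limit fell below 3.0 in about 4% of runs with normal errors and 7-8% with heavy-tailed errors, against a nominal 2.5%.
2. As a low-cost descriptive addition, report bias and A_RMS for reference SaO2 below 90% combined and for 90% and above, always with the number of pairs and subjects. Split further into the IFU bands only where numbers allow. Limit the accuracy statement to saturations with adequate data, and do not present this summary as detecting what the interval misses.
3. As a clarification only, state the limits of the range of interest, taken from the cited standards if they set them. Keep the all-pairs A_RMS under 8.3 and list pairs outside the range separately.

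The cost is SAP wording and a short analysis, with no added subjects or blood draws. The downside for the sponsor is a less favourable statement if the observed value falls at about 2.3-3.0, since it would appear with an interval that may extend above 3.
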